4.2 Scientific Rationale for Study Design

This study will assess the performance of and user experience with PureWick™ Male External Catheter when compared with a marketed comparator, Sage PrimoFit™ Male External Catheter. To best mimic potential users of the study devices, male participants ≥ 18 years of age will be enrolled. Additionally, enrollment will target approximately 50% of the sample size of men in two different BMI cohorts so that potential differences based on anatomy can be characterized. As such, participants in this study adequately represent the patients who would use the device in the hospital setting.

In the critical care setting or with patients that have limited mobility, it is commonly ordered for patients to be repositioned and turned on their side every two hours. A turning wedge is a device used by hospitals to prop the patient onto their side. Additionally, the patient is commonly ordered to elevate the head of the bed. The Primary endpoint provides a reliable and valid measurement of the efficacy related to the function of the device by capturing and weighing all urine output per void, including leakage, and dividing by the captured amount of urine in the canister. A higher captured rate constitutes a more meaningful effect. Questionnaires using a 5-point Likert scale will be administered to each participant to assess comfort, and to each HCP to assess ease of use. A higher Likert score, such as a 4 or 5, constitutes a more meaningful effect on these

secondary endpoints. Furthermore, this study seeks to understand if the PureWick™ MEC will perform effectively in male anatomy that is not compatible with traditional sheath-style condom catheters in a controlled setting.

4.2.1 Participant Input into Design

There was no participant involvement in the design of this study.

4.3 End of Study Definition

A participant is considered to have completed the study if he has completed both voids and the corresponding questionnaires.

The end of the study is defined as the date of completion of the last participant in the study.

5 STUDY POPULATION

Adult male healthy volunteers will be recruited for this study with a target of 50% of participants in each of the two BMI cohorts. Participants will be recruited from an existing pool of volunteers in a database owned by a third-party research vendor. Basic screening questions will be used to identify potential participants and full screening against inclusion/exclusion criteria will be completed on the day of enrollment.

5.1 Inclusion Criteria

In order to be eligible to participate in this study, an individual must meet all of the following criteria:

1. Adult Male Patient \geq 18 years old
2. Male anatomy at time of enrollment
3. Ability to speak and understand English
4. Willing to comply with all study procedures in this protocol
5. Able to independently void urine
6. Provision of signed and dated informed consent form

5.2 Exclusion Criteria

Participants are excluded from the study if any of the following criteria apply:

1. Urinary incontinence which does not allow the subject to spontaneously void
2. Frequent episodes of bowel incontinence
3. Has Urinary Retention
4. Has any irritation, wound, open lesion, at the application site, on the genitalia, perineum, or sacrum
5. Recent surgery of the external urogenital tract, penis, or pubic area
6. Not able to comply with study procedures independently without required assistance
7. Any other condition that, in the opinion of the investigator, would preclude them from participating in the study

5.3 Lifestyle Considerations

No restrictions are required.

5.4 Screen Failures

Screen failures are defined as participants who consent to participate in the clinical study but are not subsequently randomized into the study. Demographic information may be captured for screen failures. Screen failures will not be allowed to re-screen.

6 STUDY INTERVENTION(S)

6.1 Investigational/Test Device

The PureWick™ MEC is a commercially available device. It is a Class I, 510(k) exempt device. The device is intended for non-invasive urine output management in male patients. The PureWick™ MEC is a single-use, non-sterile device. The IFU for the PureWick™ MEC can be found in [Appendix 1](#).

6.2 Control Device/Standard of Care

The Sage PrimoFit™ is a commercially available device. It is a Class I, 510(K) exempt device. The device is intended for non-invasive external collection of urine for adult

patients with male anatomy who require urine management. The Sage PrimoFit™ is a single -use, non-sterile device. The IFU for the Sage PrimoFit™ can be found in [Appendix 2](#).

6.3 Ancillary Devices/Products

Ancillary products for this study are listed below.

- Standard suction tubing and canisters
- BBS Revolution: Bladder Scanner + Display (PD0100002)
- Absorbent under-pads
- Commercially available scales
- Clippers/trimmers
- Wipes/towels for peri-care
- Turning wedge (45-degree foam wedge)
- PPE

6.4 Device Labeling

All commercial products will be supplied as labeled by the manufacturer. The study site will document all study devices and products received.

6.5 Treatment Allocation and Measures to Minimize Bias

Known foreseeable factors that could potentially compromise the outcome of the investigation or interpretation of the results or introduce bias into the study are delineated in this section.

This is a single-blind, cross-over study in which each subject acts as his own control and therefore, the difference in treatments is derived from a within-subject comparison. This allows for better control of potential cofounders and removes the inter-subject variability from the comparison between treatment groups.

Standardized questionnaires will be used to assess participant comfort and HCP ease of use. As training level and device experience could be a foreseeable factor that could impact ease of use outcomes, HCPs will all be trained using standardized instructional videos and device IFUs.

6.5.1 Randomization

Participants will be randomized 1:1 to one of the two treatment sequences. Subjects randomized to Sequence 1 will use PureWick™ MEC first, followed by

Sage PrimoFit™. Subjects randomized to Sequence 2 will use Sage PrimoFit™ first, followed by PureWick™ MEC. Randomization will be stratified by cohorts (non-morbidly obese men: BMI <40 or morbidly obese men: BMI ≥40). This design allows for the evaluation of elements such as carryover effect, period effect, and sequence effect.

The study site will receive randomization envelopes for each cohort that are numbered in sequential order. Within each randomization envelope, a treatment sequence assignment card will be enclosed. The randomization envelopes should be opened in sequential order only when all eligibility criteria are met.

6.5.2 Blinding/Masking

Complete study blinding is not feasible due to possible HCP familiarity with the study devices and visual differences between the product packaging. As such, this is a single-blind study in which only participants are blinded to which device is which. The Investigator and Sponsor will know which device the participant is being treated with at any given time.

Blinding procedures will be reviewed at the time of site initiation by a Sponsor representative. During review of the study and the informed consent process with participants, blinding and rationale should be discussed with the participant.

Any communication to the study personnel placing the device as to the randomized treatment sequence should be done in a way as to prevent the participant from overhearing. Devices should be referred to throughout the study period as 'Device A' and 'Device B' rather than the marketed product name.

Participants will remain blinded to treatment order until the study is complete.

7 STUDY PROCEDURES AND ASSESSMENTS

Study procedures and their timing are summarized in [section 1.2](#). Protocol waivers or exemptions are not allowed. Adherence to the study design requirements, including those specified in this protocol, is essential and required for study conduct.

All screening evaluations must be completed and reviewed to confirm that potential participants meet all eligibility criteria. The investigator will maintain a screening log to record details of all participants screened and to confirm eligibility or record reasons for screening failure, as applicable.

7.1 Subject Preparation – Prior to Arrival at Site

Participants will be instructed to consume fluids prior to their scheduled visit and arrive to the site with a full bladder. Participants will be instructed to trim the hair in their pubis/peri-area prior to arrival.

7.2 Screening and Enrollment

All participants will be screened against the inclusion and exclusion criteria (see section [5.1](#) & [5.2](#)). Eligibility criteria requiring a physical exam (e.g., height, weight, skin condition) will be confirmed after enrollment prior to device placement. Participants who fail to meet eligibility criteria must not have a study device placed.

The Investigator or their designee will explain the study to the participant, answer all of the participant's questions, and obtain written informed consent before the collection of any study data or performance of any study procedures. A participant who signs an informed consent will be considered enrolled in this study.

A unique identification number will be given to study participants in sequential order. The participant number will consist of 7 digits. The first three digits will designate the site number. The alpha letter represents cohort assignment, and the last three digits will designate the participant by number in sequential order (i.e., participant number 301A101 will be the first participant in cohort A; 301A102 will be the second participant in cohort A, etc.).

7.3 Medical History / Baseline Assessments

Participant demographic information, including age at time of enrollment, race, ethnicity, and sex, will be collected at baseline. In addition, the subject's initials will be collected. Height and weight will be captured to calculate BMI.

7.4 Randomization

Subject will be 1:1 randomized to one of two treatment sequences, stratified by BMI. The study site will receive the randomization envelopes for each cohort that are numbered in sequential order. Within each randomization envelope, a treatment assignment card with randomization ID and treatment sequence assignment will be enclosed. The

randomization envelope should be opened in sequential order only when all eligibility criteria are met.

7.5 Test Procedure

1. After enrollment and randomization, the participant will be brought to the testing area and instructed to undress and put on a gown.
 - a. The bed in the test area will be set with clean sheets, a pre-weighed absorbent pad and a pre-weighed urine collection canister.
2. The Health Care Professional (HCP) will complete a visual assessment of the participant's pubic and genital region to ensure that the participant is trimmed and assess the anatomy.
 - a. Unless the participant arrives with their pubic hair pre-trimmed, the participant's pubic hair will be clipped by themselves or a trained professional.
 - b. The HCP will then complete a brief survey to assess for a buried penis and/or anatomical compatibility with traditional sheath style condom catheters for each participant. "A buried penis refers to a normal-sized phallus encompassed by either skin, subcutaneous tissue, and/or fat in the prepubic area" causing a reduced visible and/or functional length of the phallus.¹¹ for each participant.
3. The HCP will place either the PureWick™ MEC or the Sage PrimoFit™ device (depending on randomized sequence) according to the device IFU and confirm the correct placement.
4. The participant will be placed in a semi-fowler position in the hospital bed and turned to one side using a turning wedge. The HCP should reconfirm correct device placement after repositioning.
5. The HCP will ensure the collection cannister and suction tubing are connected to wall suction and the suction is set to a minimum of 40mmHg continuous suction.
6. Once setup is confirmed and the device is placed, the participant will be allowed to spontaneously void. The participant will be monitored for up to 2 hours, through one void.
7. After the void, the pre-weighed absorbent pad and urine collection canister (with lid) will be weighed and the weights will be documented in the source documents.
8. The Pure Wick MEC or Sage PrimoFit™ will be removed by the HCP according to the IFU and discarded.
9. After removal, the HCP will note any signs of irritation/injury in the perineal area.
 - a. Any unresolved erythema (redness), erythema (swelling), bleeding, injury or rash must be recorded as an Adverse Event.

10. The HCP will complete a brief survey to assess device ease of use for the participant just treated.
11. Participant will be asked not to void and to drink approximately 16 ounces of liquid.
12. The second void will be repeated in same manner as the first void using the 2nd device assigned per randomization sequence.
13. When the participant feels the need to void, the HCP will confirm via the bladder scanning that the bladder volume is $\geq 125\text{mL}$.
 - a. If the volume is determined to be inadequate, the participant will be asked to drink fluids as tolerated and re-assessed in approximately 30 minutes. If the participant does not feel comfortable waiting to void, they will be allowed to proceed with void 2.
14. After device removal, the participant will complete a brief survey to assess device comfort.
15. The HCP will complete a brief survey to assess device ease of use for the participant just treated.
16. Once the second void has completed and all surveys are completed, the participant can be discharged from the study site.

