10.3 Analysis Population

The following populations are defined:

Population	Description
Enrolled	All participants who sign the ICF.
Intent-to-Treat (ITT)	Enrolled and randomized participants.
Per-Protocol	ITT subjects who are without major protocol deviation.
ITT Subpopulation	ITT subjects who are deemed unable to use traditional sheath style condom catheters.

ITT population will be used for the primary endpoint analysis. ITT subpopulation will be used for the secondary endpoint *with* hypothesis test. Per-protocol analyses may be performed as a sensitivity analysis.

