12.4 Protocol Deviations

A protocol deviation is defined as an event where the Investigator or site personnel did not conduct the study according to the protocol.

Except when necessary to protect the life or physical well-being of a participant, protocol deviations are not permitted. The Sponsor and the investigational site's IRB/EC must be notified immediately if an emergency situation arises in which the safety of a participant may require immediate intervention different than that defined in the protocol. This must be followed by written confirmation that describes the emergency action and outcomes, within five (5) working days from the date of the emergency action in accordance with the governing IRB/EC's requirement.

It is the Investigator's responsibility to ensure that there are no deviations from the Protocol. Except in an emergency, when a protocol deviation is planned or anticipated, the Sponsor should be contacted for approval. Any and all deviations must be recorded on the appropriate CRF regardless of whether medically justifiable or sponsor approved. Upon evaluation by the Sponsor, actions may be required to prevent additional deviations, such as retraining of the site, implementation of additional site procedures, and more frequent monitoring. If these steps fail, more serious measures, up to and including termination of enrollment at the site.

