16 APPENDICES

16.1 Appendix 1: PureWick™ Male External Catheter Instructions for Use (IFU)

Instructions for Use

PUREWICK™

MALE EXTERNAL CATHETER

Male External Catheter Kit

Contents:

- 1 PureWick™ Male External Catheter
- 1 Pack Peri-Care Wipes
- 1 Drying Wipe

Setup:

1. Connect a canister to wall suction and set to a minimum of 40mmHg continuous suction. Always use the minimum amount of suction necessary.
2. Using standard suction tubing, connect the device to a collection canister.
Note: Collection canister and suction tubing are not included. If hospital policy allows and if using a graduated canister, captured urine may be used for approximate urine output measurement.

Peri-care and Placement:

[figure not shown]
[figure not shown]
3. If there is significant pubic hair, trim or clip the pubic hair. Perform perineal care using the included wipes and assess skin integrity. Follow and document per hospital protocol.
Note: Use the included drying wipe to ensure skin is dry prior to placement of the device. Moisture on skin will weaken the adhesive.
4. Orient the device, aligning drainage fitting towards the feet of the patient. Slide the opening of the device over the penis until close to the pelvic skin. Center penis within the opening. Remove adhesive liner and press the device against the pelvic skin to adhere. Ensure base has fully adhered around the base of the penis.
Note: The scrotum should not be placed inside the device.

Removal:

5. To remove the device, gently lift the top edge of the device off the skin. In a slow, downward peeling motion, remove the device. If necessary, use a warm wet compress (such as a wet washcloth) to help loosen adhesive.
Warning: To avoid potential skin injury, never pull the device directly away from the patient. Always peel in the direction from head to foot.

Maintenance:

6. Replace the device at least every 24 hours or if soiled with feces, blood, or semen.

BAIRD

Protocol Number: UCC-23AC022

CONFIDENTIAL

Version:1.0

Date: 16May2023

PUREWICK™

MALE EXTERNAL CATHETER

Indication for use:

The device is intended for non-invasive urine output management in male patients.

Contraindications:

- Patients with urinary retention

Warnings:

- Do not use on irritated or compromised skin.
- Do not cover fresh surgical wounds with the device.
- Do not use the device with any material or in any position that does not allow for sufficient airflow.

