- Step 10** Ensure adequate length of suction tubing is available. Attach suction tubing to the device at the suction tubing adapter. Ensure connection of suction tubing to device is secure and connected at all times while device is in use. Confirm there are no kinks in the tubing and that tubing does not run under the patient. (Figure 6)
 - Secure tubing per hospital protocol.
- Step 11** Set vacuum to low, continuous suction at a minimum of 60mmHG. Always use the minimum amount of suction necessary.
- Step 12** Return patient's legs to a closed position.
 - Assess device periodically to ensure proper placement, particularly after turning or repositioning patient.
 - Device can be left in place for up to 24 hours. Replace device if soiled with stool or bodily fluids other than urine. Discard device according to hospital protocol and local regulations.

Removal

- Step 1** Place the patient in the supine position and separate patient's legs.
- Step 2** Gently remove the adhesive pad from the patient's abdomen.
- Step 3** Remove the patient's penis from the chamber.
- Step 4** Gently remove the base adhesive by pulling the tabs down and away from the patient's penis.
- Step 5** Assess skin integrity and perform perineal care.
- Step 6** Disconnect device from suction tubing and discard device according to hospital protocol and local regulations.

Discontinue use

- When independent or assisted toileting is feasible.
- During patient ambulation.

Product part identification:

[figure not shown]

Figure 1

[figure not shown]

Figure 2

[figure not shown]

Figure 3

[figure not shown]

Figure 4

[figure not shown]

Figure 5

[figure not shown]
[figure not shown]

Figure 6

Manufactured for: Sage Products LLC
 [name] • [name]
 [name] • stryker.com
 Assembled in U.S.A.
 U.S. Patents: stryker.com/patents

For a French-Canadian translated version of the instructions for use contact Stryker Customer Service at [name]. In Canada, this product is not intended to be sold to the general public.

R48050

6 18029 60044 8

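### The single 40 mmHg suction floor in the test procedure matches the PureWick IFU but is 20 mmHg below the PrimoFit IFU minimum

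*Protocol*

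**What the plan says.** Four places in the Protocol bear on suction.

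- **Section 7.5, step 5.** The HCP connects the canister and tubing to wall suction and ensures that "the suction is set to a minimum of 40mmHg continuous suction". No device is named and the IFU is not mentioned.
- **Section 7.5, step 12.** "The second void will be repeated in same manner as the first void using the 2nd device assigned per randomization sequence". Step 5 therefore applies to whichever device comes second as well.
- **Appendix 1, PureWick IFU, Setup, step 1.** "Connect a canister to wall suction and set to a minimum of 40mmHg continuous suction".
- **Appendix 2, PrimoFit IFU, Placement, Step 11.** "Set vacuum to low, continuous suction at a minimum of 60mmHG. Always use the minimum amount of suction necessary".

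Neither the Protocol nor the SAP gives a separate PrimoFit setting anywhere else. Step 3 of Section 7.5 does require the HCP to place the device "according to the device IFU and confirm the correct placement", and Section 6.5 says that "HCPs will all be trained using standardized instructional videos and device IFUs".

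Step 7 has the pad and canister weights documented. No listed step has the suction reading documented.

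**The concern.** Both devices rely on suction to move urine to the canister. The gain in canister weight is the numerator of the capture rate (SAP Section 5.1), which is the primary endpoint. Step 5 is the last suction check before the void and the only one with a number in it. That number is the test device's minimum and lies below the comparator's.

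If some PrimoFit voids were run at 40 to 59 mmHg, and if capture fell as a result, the comparison would tilt toward PureWick in a trial whose success claim is PureWick superiority. The bias controls in Section 6.5 would not help. Within-subject comparison and randomised order remove subject and period effects, but this error would follow the device. The HCP setting the suction is also unblinded (Section 6.5.2).

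If the reading is not recorded at the time, it may be impossible to show afterwards that the comparator was run within its IFU. Section 11.3 itself says that missing observation data cannot be recovered from another source.

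**Working it through.** **1. Compare the floors.**

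| Device | IFU minimum | Step 5 floor | Step 5 minus IFU |
|---|---|---|---|
| PureWick | 40 mmHg (Appendix 1) | 40 mmHg | 40 − 40 = 0 |
| PrimoFit | 60 mmHg (Appendix 2) | 40 mmHg | 40 − 60 = −20 mmHg |

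The shortfall is 20/60 = 33% of the comparator's minimum. A PrimoFit setting from 40 to 59 mmHg meets step 5 and fails the IFU. A setting of 60 or more meets both.

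**2. Reproduce the plan's own power figure.** Protocol Section 10.2 and SAP Section 2.4 give n = 44, a two-sided paired t-test at 0.05, a mean difference of half the SD, and 90% power. With df = 43 the critical t is 2.017 and the noncentrality is 0.5 × √44 = 3.317. The noncentral t gives power 0.900, so the figure reproduces.

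**3. Sensitivity illustration.** The documents give neither of two quantities needed, so both are assumptions:

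- f, the share of PrimoFit voids run below 60 mmHg;
- L, the capture lost in such a void, in percentage points.

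Take the plan's example (n = 44, SD of the paired difference 10 points) and a true device difference of zero. The mean shift toward PureWick is b = f × L. When f is below 100%, mixing affected and unaffected voids raises the SD to √(100 + L² f(1 − f)). The chance of a false PureWick win is P(T > 2.017), with T noncentral t on 43 df and noncentrality (b/SD) × √44.

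| f | L (points) | b (points) | SD | Noncentrality | False PureWick win |
|---|---|---|---|---|---|
| 0, or any with L = 0 | – | 0 | 10 | 0 | 2.5% |
| 25% | 2 | 0.5 | 10.04 | 0.330 | about 5% |
| 50% | 2 | 1 | 10.05 | 0.660 | 9.4% |
| 100% | 1 | 1 | 10 | 0.663 | 9.5% |
| 100% | 2 | 2 | 10 | 1.327 | 25.4% |
| 100% | 5 | 5 | 10 | 3.317 | 90.0% |

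Simulation of the two mixed rows gives 5.0% and 9.4%. A mean shift of about 0.49 points is enough to double 2.5% to 5%. The last row is the design power under another name, since L equals the plan's example difference; it marks the far end of the range.

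**4. How a low-suction void would be classified.** Section 12.4 says: "A protocol deviation is defined as an event where the Investigator or site personnel did not conduct the study according to the protocol". A PrimoFit void at 45 mmHg complies with step 5 and arguably breaches step 3. The per-protocol set is "ITT subjects who are without major protocol deviation", and neither document defines a major deviation. The texts therefore do not settle whether such a void stays in that set.

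**The case against.** The strongest reply is that the protocol already covers this. Step 3 requires IFU placement, and in the PrimoFit IFU the 60 mmHg setting is itself a placement step. An HCP who follows the steps in order has PrimoFit at 60 or more before reaching step 5, which then passes and changes nothing. HCPs are trained on the IFUs, and the Protocol states that the devices are used as intended (Section 2.3). The PrimoFit advice to use no more suction than necessary comes straight after the 60 figure, so it points to 60 and not to 40. On this reading a PrimoFit void below 60 is a deviation that Section 12.4 requires to be recorded.

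Much of this stands. The protocol permits under-suction at step 5 but does not instruct it, and one setting can satisfy every text. It is also fair that:

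- nothing in the documents relates suction pressure to capture;
- f and L are invented inputs, and the rows with f = 100% assume that every comparator void breaches the IFU;
- the CRF pages are not available, so a suction field cannot be ruled out;
- the undefined term for a major deviation is a general gap, not one specific to suction.

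None of this removes the conflict. Steps 3 and 5 give different minimums for the same PrimoFit void. Step 5 is the later, explicit, numeric check, and it is too low for one device only. The HCP should not have to overrule the procedure from an appendix.

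**Conclusion.** The point holds: step 5 is wrong as written for the comparator, by 20 mmHg (33% of its IFU minimum), and right for the test device. Any resulting loss of capture would favour PureWick on the primary endpoint, and the crossover design would not remove it.

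Confidence is high on the mismatch in the texts. An effect on the result needs two further conditions that the documents do not establish: that comparator voids are run at 40 to 59 mmHg, and that capture falls when they are. The false-win figures, from 2.5% with no effect to 90% at the extreme, rest on assumed f and L and on the plan's example SD of 10 points. They are a sensitivity range, not an estimate. They do show that a small average loss would matter. The correction should be made before enrolment, because a suction setting that was not recorded cannot be reconstructed.

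**What to change.** 1. Reword step 5 of Section 7.5 to give device-specific floors from the appended IFUs: at least 40 mmHg for PureWick and at least 60 mmHg for PrimoFit. This change removes the conflict.
2. Record the suction reading for each void with the weights in step 7, if the CRF does not already have a field for it.
3. As supporting detail, state in the SAP that a void run below the IFU minimum of the device in use is a major deviation for the per-protocol analysis. This does not alter the primary ITT test, so it does not replace items 1 and 2.

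The cost is one protocol line, at most one source or CRF field, and one SAP line. No participants or procedures are added, and 44 evaluable subjects with 90% power in the plan's example are unchanged.
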